3.2.3 Mapping of assessments performed at Premature End of Treatment Visit

PEOT assessments will be assigned to the next scheduled site visit (following the last scheduled visit that the study participant completed prior to PEOT) where each assessment is evaluated as

per protocol. This approach means that there is a chance that PEOT data will be mapped to different visits according to the schedule of assessments.

3.3 Definition of Baseline values

Baseline will be the last available value prior to or on the same date (and time if time is collected for the individual assessment) of the first infusion of IMP in the Treatment Period, or if missing, the Screening value. Scheduled or unscheduled measurements can be used as the Baseline value. If a Baseline measurement is not available but an unscheduled measurement occurs after the planned baseline measurement time point but before dosing, then the unscheduled measurement will be used. MG-specific autoantibodies MuSK and AChR Baseline is detailed in Section 9.2.1, and ADA Baseline is detailed in Section 9.3.1.

3.4 Protocol deviations

Important protocol deviations (IPDs) are deviations from the protocol which potentially could have a meaningful impact on study conduct or on the primary efficacy, key safety, or PK/PD outcomes (if applicable) for an individual study participant. The criteria for identifying important protocol deviations will be defined within the appropriate protocol-specific document. Important protocol deviations will be reviewed as part of the ongoing data cleaning process and data evaluation. All IPDs will be identified and documented prior to unblinding and will be utilized to decide, which data will exclude study participants from the Pharmacokinetic Per-Protocol Set (PK-PPS).

3.5 Analysis sets

3.5.1 Enrolled Set

The Enrolled Set (ES) will consist of all study participants who have signed the informed consent.

3.5.2 Randomized Set

The Randomized Set (RS) will consist of all study participants who were randomized, using the treatment assigned instead of the actual treatment received.

3.5.3 Safety Set

The Safety Set (SS) will consist of all randomized study participants who received at least one dose of IMP and analyzed according to the actual treatment the participants received.

3.5.4 Pharmacokinetic Per-Protocol Set

The PK-PPS will consist of a subset of the SS, consisting of those study participants who received at least 1 dose of rozanolixizumab, had at least 1 quantifiable concentration of rozanolixizumab, and no important protocol deviations affecting the PK variable, as confirmed during a pre-analysis review of the data prior to database lock. Post-Baseline deviations will not necessarily lead to total exclusion of a study participant from the PK-PPS but may lead to exclusion of specific data.

3.5.5 Full Analysis Set

The Full Analysis Set (FAS) will consist of all study participants in the RS, who have a Baseline and least 1 post-Baseline MG-ADL measurement.

3.6 Treatment assignment and treatment groups

If after unblinding it is determined that study participants at any time receive incorrect treatment from their randomized assignment, then for safety and PK/PD analyses these study participants will be reallocated to the appropriate treatment group. For example, if study participants randomized to placebo received rozanolixizumab, then for the safety and PK/PD analyses, these study participants will be reallocated to rozanolixizumab. If a study participant received both doses of rozanolixizumab at different time points, then the study participant will be allocated to the higher dose (i.e. [REDACTED]) group in the safety and PK/PD analysis. Study participants randomized to rozanolixizumab will only be reallocated to the placebo treatment group if they never received rozanolixizumab.

Efficacy data will be summarized by randomized treatment group as shown below:

- Placebo
- Rozanolixizumab [REDACTED] equivalent, displayed as RLZ [REDACTED]
- Rozanolixizumab [REDACTED] equivalent, displayed as RLZ [REDACTED]

3.7 Center pooling strategy

It is planned to recruit study participants in North America, Europe, and Asia in this study, with possible extension to other regions and countries. The data from all sites will be pooled for analyses. Geographic regions and countries are categorized as following,

- Asia (excluding Japan): Taiwan
- Europe: Belgium, Czech Republic, Germany, Denmark, Spain, France, United Kingdom, Georgia, Hungary, Italy, Poland, Russian Federation, Serbia
- North America: Canada, United States
- Japan: Japan

3.8 Coding dictionaries

Adverse events (AEs) and medical histories will be coded using version 24.0 or later of the Medical Dictionary for Regulatory Activities (MedDRA®).

Medications will be coded according to B3 version Mar 2021 or later of the World Health Organization Drug Dictionary (WHODD).

3.9 Changes to protocol-defined analyses

- Mixed model for repeated measures (MMRM) analysis of covariance (ANCOVA) is specified as the model used for the analysis of primary endpoint. In the SAS, MMRM is used as the model only.
- ADDPLAN MC is specified in the protocol for making determinations from the interim analysis. However, SAS or the R package for Adaptive Clinical Trials (RPACT) will be used instead. For the purposes of this analysis, these packages will provide the same functions as ADDPLAN MC.

- The treatment group by week interaction term is specified to be used in the model of analysis of primary efficacy endpoint. In the SAP, treatment group by day interaction will be used instead.
- The Full Analysis Set (FAS) will consist of all study participants in the RS, who have a baseline and at least one post-Baseline MG-ADL measurement. The protocol incorrectly states this as SS.
- Stratification factors used in statistical modeling, such as muscle specific kinase [MuSK(+/-)] and acetylcholine receptor [AChR(+/-)] are defined in the SAP as two binary variables, instead of one binary variable [MuSK(+) or AChR(+)] – this is to account for study participants who may be double-positive.
- Estimands and Intercurrent event handling strategies have been updated based on regulatory feedback.
- Minimal Symptom Expression (MG-ADL score of 0 or 1) at any time up to and include both treatment and observation phase, where the protocol only states to include up to Day 43 (Visit10).
- Potential Hy's Law has been updated to Alanine Aminotransferase (ALT) or Aspartate Aminotransferase (AST) > 3x Upper Limit of Normal (ULN) and total Bilirubin (TBL) > 2x ULN, and Alkaline Phosphatase (ALP) < 2x ULN.
- Calculation of Low-density lipoprotein (LDL) will follow Friedewald equation, where LDL in mmol/L = TC - HDL - TRIG/2.22; LDL in mg/dL = LDL = TC - HDL - TRIG/5 (if all values are in mg/dL). This formula is applicable only if Triglycerides is less than or equal to 400 mg/dL (4.52 mmol/L).
- MG-C responders are defined as at least a 3-point improvement (decrease) from Baseline instead of 5-point improvement.
- Patient Global Impressions of Severity (PGI-S) at each scheduled assessment during the Treatment and Observation Periods instead of change from Baseline of PGI-S.

4 STATISTICAL/ANALYTICAL ISSUES

4.1 Adjustments for covariates

The efficacy analyses will be adjusted for the following covariates:

- Baseline MG-ADL score,
- Region (North America, Europe, and Asia [excluding Japan], Japan),
- Stratification factors – MG-specific autoantibodies, including muscle specific kinase [MuSK(+/-)] and acetylcholine receptor [AChR(+/-)], both as binary variables.

In statistical modeling, the stratification factors MuSK(+/-) and AChR(+/-) will be based on the values from MG-specific autoantibody assessment at Baseline. In case Baseline MG-specific autoantibody result is missing (and not resolved after data queries), a post-Baseline measurement may be used. If this is not available, then the historical result will be used in the model; if the historical result is missing as well, the stratification factor from IWRS randomization file will be used to determine values used in the model (i.e., if the stratification is MuSK in IWRS, then

MuSK(+/-) will be imputed as positive, otherwise negative; similarly, if stratification factor is AChR in IWRS, then AChR(+/-) will be imputed as positive, otherwise negative).

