Day (days) ^c	-28 to -1	1	3(±1)	8(±2)	15(±2)	22(±2)	24(±1)	29(±2)	36(±2)	43(±2)	57(±3)	71(±4)	85(±3)	99(±4)
Plasma complement levels (C3a and C5a) ⁿ		X							X					
MGFA classification	X	X								X				X
QMG scale	X	X		X	X	X		X	X	X		X		X
MG-C scale	X	X		X	X	X		X	X	X		X		X
MG-ADL	X	X		X	X	X		X	X	X	X	X	X	X
MG Symptoms PRO	X	X		X	X			X		X		X		X
PGI-S	X	X			X			X				X		X
PGI-C					X			X				X		X
EQ-5D-5L		X								X				
MGII ^o		X								X				
MG-QOL15r		X								X				
Study drug discontinuation criteria				X	X	X		X	X					
Study withdrawal criteria	X	X	X	X	X	X	X	X	X	X	X	X	X	X

AChR=acetylcholine receptor; ADA=anti-drug antibody; AE=adverse event; AESM=adverse events of special monitoring; BL=Baseline; C-SSRS=Columbia Suicide Severity Rating Scale; ECG=electrocardiogram; EQ-5D-5L=EuroQol-5D-5L; EOS=End of Study; EOT=End of Treatment; GI=gastrointestinal; HIV=human immunodeficiency virus; IgA=immunoglobulin A; IgE=immunoglobulin E; IgG=immunoglobulin G; IgM= immunoglobulin M; IGRA=interferon-gamma release assay; IMP=investigational medicinal product; INR=international normalized ratio; IRT=interactive response technology; MG=myasthenia gravis; MG-ADL=myasthenia gravis-Activities of Daily Living; MG-C=Myasthenia Gravis Composite; MGFA=Myasthenia Gravis Foundation of America; MGII=Myasthenia Gravis Impairment Index; MG-QOL15r=Myasthenia Gravis Quality of Life; MuSK=muscle-specific kinase; PEOT=premature end of treatment; PGI-C=Patient Global Impression of Change; PGI-S=Patient Global Impression of Severity; PK=pharmacokinetics; PTT=partial thromboplastin time; PRO=patient-reported outcome; QMG=Quantitative Myasthenia Gravis; TB=tuberculosis; V=Visit

^a This visit can be scheduled as a home visit, unless the study participant prefers to attend the site.

^b This visit will be a virtual visit, unless the study participant prefers to attend the site.

- ^c A visit window of ± 1 day is allowed for V3 and V7. A visit window of ± 2 day is allowed for all dosing visits. The visit window of ± 2 days is relative to the first dosing visit date. However, there should be a minimum interval of 5 days and maximum interval of 9 days as compared to the previous dose. A visit window of ± 3 days is allowed for V11 and V13. A visit window of ± 4 days is allowed for V12 and V14.
- ^d Refer to Section 1.4.
- ^e Only weight will be repeated at Baseline (V2).

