8.2.2 Primary analysis of the primary efficacy endpoint

The primary analysis is based on the RS under the hypothetical & treatment policy strategy (see details in [Section 8.1](#)). Any missing MG-ADL scores (including missing data after the intercurrent events) will be handled based on maximum likelihood estimation method under MAR assumption.

A stage-wise MMRM with treatment group, Baseline MG-ADL score, region, stratification factor(s) including MuSK(+/-) and /or AChR(+/-), and treatment group by day (interaction term) as fixed factors and study participant as a random effect. The MMRM will include Days 8, 15, 22, 29, 36 and 43.

The model will utilize an unstructured covariance pattern for the repeated measures. If the model does not converge using the unstructured pattern, then an autoregressive covariance structure

will be used. The Kenward-Roger approximation will be used to estimate the denominator degrees of freedom.

For each stage, the least squares means (LSMs) of each treatment group, and the least squares mean differences (LSMDs) between each dose group and placebo will be reported for Day 43 (Visit 10), along with the corresponding 2-sided 97.5% CIs and p-values.

The study follows a 2-stage group sequential adaptive design using combination test (Lehmacher and Wassmer, 1999) based on the inverse-normal method of combining independent stagewise p-values (Hedges and Olkin, 1985)

The analysis takes into account that the study is a 2-stage group sequential adaptive design assuming equal weighting of each stage, with weights = $1/\sqrt{2}$:

- Stage 1 – Cohort up to the formal IA
- Stage 2 – Cohort post-IA

The following sequential test statistic will be used to test the global null hypothesis at the end of stage 2:

$$T = \sum_{i=1}^2 w_i \phi^{-1}(1 - p_i)$$

Where subscript $i = 1, 2$ represents the stage, p_i represents the appropriate multiplicity adjusted p-value at stage i (for example at stage 1, $p_1 = \min(2 * p_{\min}, 1)$ where p_{\min} is the minimum of the two nominal p-values), the weights $w_{ki} = 1/\sqrt{2}$ satisfy $\sum_{i=1}^2 w_{ki}^2 = 1$ and ϕ^{-1} is the inverse cumulative standard normal distribution function. The test statistic T and $z = \phi^{-1}(1 - p_i)$ have a standard normal distribution, (Lehmacher and Wassmer, 1999).

The combined p-value (2-sided) for the 2 stages, which tests the global null hypothesis, can be calculated by:

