8.2.4 Supplementary analyses of the primary efficacy endpoint

8.2.4.1 Supplementary Analysis #1

The first supplementary analysis will be performed based on the RS, using the composite strategy (see details in [Section 8.1](#)). A trimmed mean approach, where missing data are assumed to be missing not at random (MNAR), will be used to impute missing MG-ADL scores (including the intercurrent events) with the worst score of the MG-ADL questionnaire.

The trimmed mean approach will be applied for each stage separately as follows:

1. Perform an analysis using ANCOVA model with treatment group, Baseline MG-ADL score, region, stratification factors (MuSK+/- and AChR+/-) as fixed effects excluding any study participants with missing data at Day 43 or who experienced an intercurrent event by Day 43.
2. Retain the coefficients from the model for Baseline MG-ADL score, region, and stratification factors (MuSK+/- and AChR+/-).
3. Calculate the adjusted endpoint for each study participant as based on the raw CfB and coefficients calculated from the ANCOVA in Step 1: $\text{Adjusted CfB} = \text{Raw CfB} - \text{Stratification Coefficient} * \text{Stratification (AChR/ MuSK)} - \text{Baseline Score Coefficient} * \text{Baseline MG-ADL score} - \text{Region Coefficient} * \text{Region}$.
4. Identify any study participants with missing data at Day 43 and any study participants who experienced any intercurrent event by Day 43. A worst score (i.e., 24) will be imputed for these study participants at Day 43 in order to flag them as worse responders than any subject who completes.
5. Determine the trim fraction to be used. This will be the maximum of dropout and intercurrent event rate in each of the three treatment groups. For example, if the rate of dropout/IE in the three groups is 10, 15 and 20% then the worst 20% of each group will be the trimmed.
6. Sort each treatment group in ascending order by adjusted endpoint Day 43 MG-ADL score and trim equal fractions from each treatment group that was calculated in Step 5 from the bottom.

7. Calculate the mean adjusted CfB score of the trimmed sample for each treatment group and the difference between trimmed means of each rozanolixizumab group and placebo.

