8.3.2 Change from Baseline to Day 43 (Visit 10) in MG-C score

The complete list of MG-C items and scores are provided in [Table 13–2](#). The total score will be calculated according to the rules set down in [Section 13.2](#). This total score will be used to calculate change from Baseline, in summaries and for efficacy analysis.

The following analyses will be performed:

- Secondary: The same approach as specified in [Section 8.2.2](#) will be implemented.
- Sensitivity: The same approach as [Section 8.2.3.2](#) will be applied.
- Supplemental: The same approach as [Section 8.2.4.1](#) will be applied. The worst MG-C total score is 50.

- Additional: The same approach as [Section 8.2.5](#) will be applied.
- Exploratory: The same approach as [Section 8.2.6](#) will be applied.

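### As written, the models for MG-C, QMG and the three MG Symptoms PRO scores adjust for Baseline MG-ADL and not for the endpoint's own baseline; this would usually cost some precision, of unknown size

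*SAP*

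**What the plan says.** SAP 4.1 gives one covariate list under "The efficacy analyses will be adjusted for the following covariates": Baseline MG-ADL, region, and MuSK and AChR status. SAP 8.2.2 specifies "A stage-wise MMRM with treatment group, Baseline MG-ADL score, region, stratification factor(s") and "treatment group by day (interaction term) as fixed factors". Only treatment has a by-day term, so Baseline MG-ADL has one slope shared by all visits. Protocol 9.4.1 describes the same model with week in place of day.

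For MG-C, SAP 8.3.2 reads "Secondary: The same approach as specified in" Section 8.2.2, and 8.3.3 to 8.3.6 repeat this for QMG and the three PRO scores. Protocol 9.4.2 likewise applies the primary model to every continuous secondary endpoint. SAP 8.3.2 to 8.3.6 do state an endpoint-specific worst score (50, 39 or 100) but never an endpoint-specific baseline covariate. SAP 3.9 lists no change on this point.

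**The concern.** For a change score, the strongest baseline predictor is usually the baseline of that same score. Baseline MG-ADL is only a proxy for Baseline QMG, MG-C or a PRO domain. If own baseline is left out, variance that could be explained stays in the residual.

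These five scores are all of the formally tested secondary endpoints. SAP 4.6 tests them in series for each dose, so a missed MG-C or QMG test ends that dose's sequence. SAP 4.4.1 powers the design on MG-ADL only.

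The text also leaves the programmer a choice in a confirmatory model: fit Baseline MG-ADL as written, or assume that a swap was meant.

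**Working it through.** **Can the cross-reference be literal?** Not fully.
- SAP 8.2.2 states "The MMRM will include Days 8, 15, 22, 29, 36 and 43". In the Protocol 1.3 schedule, the "MG Symptoms PRO" row is marked in the Treatment Period after Baseline only at Visits 4, 5, 8 and 10 (Days 8, 15, 29 and 43).
- The J2R imputation model in SAP 8.2.3.2 lists only MG-ADL variables.
- The trimmed-mean analysis in SAP 8.2.4.1 begins "Perform an analysis using ANCOVA model with treatment group, Baseline MG-ADL score, region", and step 6 says "Sort each treatment group in ascending order by adjusted endpoint Day 43 MG-ADL score". Both are reused for the other scores.

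So some adaptation was expected, but none is written for the baseline term.

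**The plan's own figures.** SAP Table 2-1 concerns MG-ADL, whose own baseline is in the model. A simulation of the two-stage design reproduced the 10 scenarios tried (scenario 7: power 0.949 against 0.943), with every power within 2 points. The present point does not change them. No SD, effect or power is given for the five scores, so every input below is an assumption.

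**Set-up.** B is the own baseline (SD 1) and A is Baseline MG-ADL. rho is the correlation of B with the Day 43 score, r the correlation of A with B, and k the ratio of Day 43 SD to baseline SD, rising linearly over visits. A relates to later scores only through B. C is the change score. Data are complete and the covariance is unstructured.

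**Single-visit formula.**
- A only: k² + 1 − 2k·rho − r²(k·rho − 1)²
- With B: k²(1 − rho²)

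At rho = r = 0.5:
- k = 1: 0.9375 / 0.75 = 1.25
- k = 1.2: 1.20 / 1.08 = 1.11
- k = 1.4: 1.5375 / 1.47 = 1.05

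**Planned MMRM with a shared slope.** Under AR(1)-type decay, corr = rho^(|t − s|/42 days). The large-sample fit iterates slope = [1′S⁻¹Cov(C, A)] / [Var(A)·1′S⁻¹1] and S = Var(C − A·slope). The Day 43 element of S is then compared with the model that adds B by day, whose residual is k²(1 − rho²). Illustrative power is Φ((2.2414 + 1.2816)/√ratio − 2.2414), starting from 90% at 2-sided 0.025. The last column is 60/ratio.

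| k | Planned | Own baseline by day added | Ratio | 90% power becomes | 60 per arm equals |
|---|---|---|---|---|---|
| 1 | 0.9705 | 0.75 | 1.29 | 80.4% | 46.4 |
| 1.2 | 1.223 | 1.08 | 1.13 | 85.8% | 53.0 |
| 1.4 | 1.552 | 1.47 | 1.06 | 88.2% | 56.8 |

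The four PRO visits give the same ratios. Equal correlation at all visits gives 1.25, 1.11 and 1.05.

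**Range (AR(1)).** For rho and r from 0.3 to 0.7 the ratios are 1.14–1.51, 1.03–1.30 and 1.00–1.18 at the three values of k. At rho = r = 0.7 with k = 1.4 the ratio is 1.00. On a wider grid (rho, r 0.3–0.8, both correlation forms, A allowed its own relation to later scores) it ran from 0.97 to about 2.0, with a median near 1.1.

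**The form of the addition matters.** At rho = r = 0.7, corr(A, Day 43) = 0.35, k = 1, AR(1), the ratio is 0.87 if B replaces A, 0.92 if B is added with one shared slope, and 1.03 if B is added by day. In other assumed cases the shared-slope addition falls to 0.84.

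**Small-sample check.** One stage with three arms of 30, AR(1), 6,000 replicates, gave 1.27, 1.08 and 1.04. That run entered both baselines by day, so it only approximates the recommended model.

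**Validity.** In 5,000 simulated single-visit trials with complete data (60 per arm, rho = r = 0.5), the mean null estimate was about −0.001 with A alone. Type I error was 0.027 with either baseline as covariate, at nominal 0.025.

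**The case against.** A reader might infer that SAP 4.1 rules out own-baseline adjustment. It does not: it is silent. Nor is 4.1 applied to the letter elsewhere. The responder logistic model (8.3.1) adds region only if it is significant in the primary analysis, the Cox model (8.4.3) has no Baseline MG-ADL term, and the rescue-therapy comparison (8.4.1) is an unadjusted chi-squared test. The list may have been written with the primary endpoint in mind and own baseline simply assumed.

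The correlations, SD ratio and covariance form are all assumed. The entry rules (QMG of at least 11; no Grade 3 oropharyngeal or respiratory weakness) narrow baseline scores, which makes k above 1, and so the smaller losses, plausible. The power column is a fixed-sample approximation, whereas the tests combine two stage-wise p-values. The by-day baseline term appears nowhere in the SAP, and a like-for-like shared slope can lose precision. Convergence with the extra terms was not examined.

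All of this stands. It limits the claim to an unspecified term with a usual but uncertain cost. It does not remove the gap, because these sections adapt the worst score to each endpoint and leave the baseline covariate unadapted.

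**Conclusion.** The point holds as a precision and specification issue. Following the text would usually widen the confidence intervals of the five tested secondary endpoints. The central assumed cases give a variance ratio of 1.06 to 1.29; the wider range runs from slightly below 1 (0.97) to about 2.0. The documents cannot narrow this.

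Two stronger readings are not supported. One is that the secondary tests are biased or have inflated type I error: randomisation protects the contrast in large samples with complete data. The check does not extend to data set to missing after rescue, which rest on the SAP's MAR assumption. The other is that the secondary endpoints are materially underpowered: no effect, SD or power is stated for them, so the effect on the testing sequence cannot be quantified. The MG-ADL analyses are not affected.

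**What to change.** - In SAP 4.1 and 8.3.2 to 8.3.6, and Protocol 9.4.2, state that each continuous secondary model also includes that endpoint's own baseline. Keep Baseline MG-ADL; add rather than swap.
- Preferably enter own baseline with its interaction with day, since a single shared slope can lose precision.
- For the reused trimmed-mean ANCOVA (8.2.4.1), add the endpoint's own baseline and rank on that endpoint's adjusted score.
- For the reused J2R imputation (8.2.3.2), use the endpoint's own baseline and post-baseline scores at its scheduled visits (PRO: Days 8, 15, 29 and 43). Give the PRO MMRM the same visit list.
- Leave the MG-ADL analyses unchanged.

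The cost is a few sentences and some added covariates; the data are already collected. The by-day form uses up to six model degrees of freedom per stage (four for the PRO scores), and the secondary model then differs slightly from the primary.
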